9.4.4. Physical Examination

A complete or directed physical examination will be conducted according to the Schedule of Activities (Section 2).

9.4.5. Safety Monitoring

The sponsor will monitor safety data throughout the course of the study periodically will review evolving aggregate safety data within the study through appropriate methods..

9.4.5.1. Hepatic Safety

If a study participant experiences elevated ALT $\geq 3X$ ULN, ALP $\geq 2X$ ULN, or elevated total bilirubin $\geq 2X$ ULN, liver tests ([Appendix 4](#)) should be repeated within 3 to 5 days including ALT, AST, ALP, TBL, direct bilirubin, gamma-glutamyl transferase (GGT), and creatinine kinase to confirm the abnormality and to determine if it is increasing or decreasing. If the abnormality persists or worsens, clinical and laboratory monitoring should be initiated by the investigator based on consultation with the Lilly medical monitor. Monitoring should continue until levels normalize and/or are returning to approximate baseline levels.

Additional safety data should be collected if 1 or more of the following conditions occur:

- elevation of serum ALT to $\geq 5X$ ULN on two or more consecutive blood tests
- elevated serum TBL to $\geq 2X$ ULN (except for cases of known Gilbert's syndrome)
- elevation of serum ALP to $\geq 2X$ ULN on 2 or more consecutive blood tests

- participant discontinued from treatment due to a hepatic event or abnormality of liver tests
- hepatic event considered to be a SAE.

9.5. Pharmacokinetics

For all participants, blood samples of up to 3 mL each for the determination of the concentrations LY3526318 and metabolite(s) of interest will be collected at time points specified in the Schedule of Activities (Section 2). Instructions for the collection and handling of blood samples will be provided by the sponsor.

Sampling times for PK evaluation are provided as a guidance to be adhered to as closely as possible. The actual date and time (24-hour clock time) of each sample collection must be recorded. Pre-dose samples should be obtained between waking up and dosing.

A maximum of 3 additional PK samples may be drawn at other time points during the study, if warranted and agreed upon by both the investigator and the sponsor. A PK sample should be obtained at the early termination visit, if applicable.

Plasma sample analyses of LY3526318 and possible metabolite(s) of interest will be performed using validated procedures and methods. Placebo samples are not planned to be analyzed.

Bioanalytical samples collected to measure study drug concentrations will be retained for a maximum of 1 year following last participant visit for the study.

9.6. Pharmacodynamics

9.6.1. *Dermal Blood Flow (DBF) Measurements by Laser Doppler Imaging (LDI) and Laser Speckle Contrast Imaging (LSCI)*

Dermal blood flow will be measured at visits and time points as specified in the Schedule of Activities (Section 2). All measurements for assessment should be performed while the participants are resting in a supine position on a comfortable bed in a quiet, ambient temperature-controlled room after at least 30 minutes acclimatization period.

Measurements of DBF will be taken with or without the application of a reactive agent to the skin. Based on the presumptive mechanism of action for LY3526318, CA will be used as the reactive agent to induce DBF.

Two methods will be used to measure DBF at each time point: DBF measurements from LDI (PeriScan PIM 3 system, Perimed, Stockholm, Sweden) and LSCI (PeriCam PSI System, Perimed, Stockholm, Sweden). The LDI assessment will be performed following LSCI assessment. The screening LDI measurements will be used to determine study eligibility.

Given that an upper extremity (forearm) requires approximately 5-days to recover from a reactive DBF measurement, the schedule between the screening and first study drug administration should account for this frequency limitation. During the first period, the extremity used for the first post-dose DBF measurements is chosen and the contralateral forearm

will be used for the 24-hour post-dose time point. Subsequent study periods should use the same schedule of DBF based on forearm and time point.

During each visit (screening and study periods), each patient will undergo at least 30 minutes acclimatization and placement of 3 rubber O-rings on the volar surface of the forearm. Prior to study drug administration, a pre-drug DBF will be collected without CA. For each time point following study drug administration, pre-CA measurements will be performed for the areas defined by the rings within 10 minutes before CA application. After the pre-CA measurements, a 20 μ L topical dose of 10% CA will be applied in the proximal O-ring of the participant's forearm. Using the same procedure, a 20 μ L topical dose of 3% CA will be applied in the medial ring, followed by a 20 μ L topical dose of the vehicle solution to the distal ring. LDI/LSCI measurements will again be performed approximately 20 minutes after CA and vehicle applications. Specific details of the procedure will be agreed upon and documented between the sponsor and investigator and research staff operating the equipment.

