17.2.2 Statistical Analysis

An analysis of variance (ANOVA) will be performed on the percentage change (pre- to post-CA) at time points 3 h and 24 h post-dose using PROC MIXED in SAS. The percentage change will be used untransformed in the analysis. The model will include fixed effects for treatment, period, sequence, time and treatment*time interaction and a random effect for subject within sequence. The analysis will be done for each, method and CA concentration separately. From this model the least-squares means (LSMeans) for each treatment (including placebo) and the difference of the LSMeans for each of the active treatments with placebo at 3 h and at 24 h post-dose and the corresponding P value will be estimated for each method and CA concentration.

In the summary of the statistical analysis, it will be indicated that the result for LDI, 3 hours post-dose is the primary end point.

In SAS code:

```

proc mixed data=dbf;
  by CAconc method;
  class subject trtan time           period seq;
  model pchg = trtan time trtan*time period seq;
  random subject(seq);
  lsmeans trtan*time ;
  /*estimates*/
run;
quit;

```

For each of the active dose levels and CA concentrations, a decrease relative to placebo of the percentage change (pre- to post-CA) with a P value below (0.05/3) will be considered statistically significant.

Additionally, the same model (with fixed effects for treatment, period, sequence, time and treatment*time interaction and a random effect for subject within sequence) will be applied to the absolute values for each method and CA concentration separately, using data from all time points (i.e. pre study drug, 3 h pre- and post-CA, 24 h pre- and post-CA). From this model, using the absolute values, LSMeans and the differences with 90% CI and P-value will be estimated for each method and CA concentration for the following comparisons:

#	LSMean (absolute value) of	Compared with LSMean (absolute value) of
1	D1 post-CA at 3 h	Placebo post-CA at 3 h
2	D2 post-CA at 3 h	Placebo post-CA at 3 h
3	D3 post-CA at 3 h	Placebo post-CA at 3 h
4	D1 post-CA at 24 h	Placebo post-CA at 24 h
5	D2 post-CA at 24 h	Placebo post-CA at 24 h
6	D3 post-CA at 24 h	Placebo post-CA at 24 h
7	Placebo pre-CA at 3 h	Placebo pre study drug at 0 h
8	D1 pre-CA at 3 h	D1 pre study drug at 0 h
9	D2 pre-CA at 3 h	D2 pre study drug at 0 h
10	D3 pre-CA at 3 h	D3 pre study drug at 0 h
11	Placebo pre-CA at 24 h	Placebo pre study drug at 0 h

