12	D1 pre-CA at 24 h	D1 pre study drug at 0 h
13	D2 pre-CA at 24 h	D2 pre study drug at 0 h
14	D3 pre-CA at 24 h	D3 pre study drug at 0 h

In SAS code:

```

proc mixed data=dbf;
  by CACconc method;
  class subject trtan time           period seq;
  model aval = trtan time trtan*time period seq;
  random subject(seq);
  lsmeans trtan*time ;
  /*estimates*/
run;
quit;

```

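### The planned tests of resting flow (SAP 17.2.2, rows 7-14) are all within-treatment changes from one 0 h value; no dose-minus-placebo contrast is planned, and some rows may also carry a forearm difference

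*Protocol*

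**What the plan says.** **Forearms.** In Protocol 9.6.1 the arm for the 3 h measurement is settled in Period 1: "the extremity used for the first post-dose DBF measurements is chosen and the contralateral forearm". The second arm is kept for the measurement at 24 h. For later periods, "Subsequent study periods should use the same schedule of DBF based on forearm and time point". The section gives no rule for picking the side.

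**Pre-drug value.** The same section says "Prior to study drug administration, a pre-drug DBF will be collected without CA", and describes "placement of 3 rubber O-rings on the volar surface of the forearm", in the singular. It does not name the forearm used at 0 h.

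**Model.** The absolute-value model in SAP 17.2.2 is fitted "using data from all time points (i.e. pre study drug, 3 h pre- and post-CA, 24 h pre- and post-CA"). That is five time levels, one of them pre-drug. The terms are treatment, period, sequence, time, treatment by time, and a random subject effect. There is no forearm term.

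**Comparisons.** Rows 1-6 compare each dose with placebo, post-CA, at 3 h and 24 h. Rows 7-10 compare pre-CA at 3 h, and rows 11-14 pre-CA at 24 h, with the same treatment's 0 h value. Row 11, for example, takes "Placebo pre-CA at 24 h" and row 12 takes "D1 pre-CA at 24 h", each against its own 0 h value. Every row gets a 90% CI and a P-value.

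**The concern.** The primary variable is the percentage change from pre-CA to post-CA flow, 100 × (post/pre − 1). Resting flow is its denominator. If the drug raised resting flow and left post-CA flow alone, the percentage would fall without any fall in CA-stimulated flow. Someone interpreting a positive result will want to know whether resting flow differed between drug and placebo.

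Rows 7-14 are the only planned inference on resting flow, and they do not answer that question. A within-treatment change from 0 h contains whatever happens to resting flow over 3 hours of fasting and confinement, or by the next day, whatever was given. The opposite-forearm schedule may add a side difference. The randomized comparison, which would remove all of these, is used for post-CA flow (rows 1-6) but not for resting flow.

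**Working it through.** The documents give no power or error rate for rows 7-14, so there is no stated figure to reproduce.

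**1. What each contrast estimates.** For treatment k, let T(t) be the mean change in resting flow from 0 h to time t that is common to all treatments, D(k,t) the drug effect at time t (zero for placebo and at 0 h), and A(t) the mean difference between the forearm used at t and the forearm used at 0 h.

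- Rows 7-10 estimate T(3) + D(k,3) + A(3).
- Rows 11-14 estimate T(24) + D(k,24) + A(24).
- Dose minus placebo, pre-CA at the same t, estimates D(k,t). T and A cancel because the forearm-by-time schedule is the same in every period.

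T is present in all eight rows regardless of forearm. The effect of A depends on the 0 h forearm:

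| 0 h value taken on | Rows 7-10 | Rows 11-14 |
|---|---|---|
| the 3 h forearm | no arm term | full arm difference |
| the 24 h forearm | full arm difference | no arm term |
| both, averaged | half | half |
| both, matched by arm | none | none |

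The last case needs two 0 h values, and the SAP's time factor has only one pre-drug level.

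**2. Precision.** With residual SD σ and 16 participants, the standard error under the SAP model is σ√(2/16) = 0.354σ, both for rows 7-14 and for dose minus placebo at one time point. A difference of changes, (dose at t − dose at 0 h) − (placebo at t − placebo at 0 h), also removes T and A, but its standard error is √2 times larger: 0.500σ.

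**3. Illustrative size of a forearm shift.** Assume no drug effect, T = 0, and a mean arm shift of d residual SDs on the affected rows. The 90% CI excludes zero when |t| exceeds the 95th percentile of t. The non-centrality is d/0.354, which is 0.71, 1.41 and 2.83 for d = 0.25, 0.5 and 1.0.

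| Assumptions | No shift | 0.25 SD | 0.5 SD | 1.0 SD |
|---|---|---|---|---|
| All 16 shifted the same way, equal variances, 42 df | 10% | 18% | 40% | 87% |
| Same, 282 df | 10% | 18% | 41% | 88% |
| Sides split 12/4, so mean shift (12 − 4)/16 = 0.5d | 10% | 12% | 18% | 40% |
| Sides split 8/8, mean shift 0 | 10% | 10% | 10% | 10% |
| All 16 shifted, resting SD half the post-CA SD, 282 df | 1% | 4% | 15% | 65% |

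The 42 df are those of a single-time-point analysis: 64 − 1 − 15 subjects − 3 periods − 3 treatments. The five-time-point model has 320 − 1 − 15 − 3 − 19 treatment-by-time cells = 282. The choice barely matters.

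In the last line the model pools three resting and two post-CA levels. With a post-CA SD of 1, the pooled SD is √((3 × 0.25 + 2 × 1)/5) = 0.742, against a true resting SD of 0.5. The resting-row intervals are therefore too wide, and shifts are expressed in resting SDs.

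A simulation of paired changes with the 0 h value on the 3 h arm (4,000 runs per shift, all 16 shifted) gave 18%, 38% and 86% for a 24 h row. The 3 h row stayed near 10%, and the placebo-referenced 24 h change stayed at 10-11% with bias near zero.

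**The case against.** The strongest objection concerns the forearm. A reader might infer that one set of rows is confounded with arm whatever is done, and that false-positive rates of 18% to 87% follow. The documents do not support that. They give neither the 0 h forearm nor the rule for choosing sides, and Protocol 9.6.1 leaves procedural details to be agreed and documented separately. A left/right difference cancels from the LSMeans if sides are balanced across participants, and halves at a 12/4 split. The size of the shift has no anchor in the documents, and the nominal 10% itself requires equal residual variances at rest and after CA. This part of the objection stands, and the figures are illustrations only.

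It can also be said that the SAP never calls these rows drug effects. Its significance rule covers the percentage change against placebo, and resting flow is not a listed endpoint. Rows 7 and 11 show placebo's change with its own CI, so a shift common to all treatments would be visible there. That is true, but comparing two within-treatment rows by eye gives no estimate, CI or P-value for their difference.

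Time of day is a weak argument for the 24 h rows: Protocol 7.2.1 has doses given at about the same times each day, so 0 h and 24 h fall at a similar clock time. Next-day effects remain in those rows, and time since dosing in the 3 h rows.

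Finally, a reader might infer that the primary analysis shares the forearm problem. It does not: drug and placebo are compared at 3 h on the same scheduled forearm, each as a change from a pre-CA value taken at that same session.

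**Conclusion.** The point holds for supplementary analyses. The firm part, which needs no assumption about forearms, is that rows 7-14 cannot separate a drug effect on resting flow from time-related change, and that no planned contrast estimates drug minus placebo on resting flow. The conditional part is that at least one set of rows may carry a forearm difference; this requires an unbalanced choice of side and a 0 h value not matched by arm. If it occurs, an affected row's false-positive rate could lie anywhere from about the nominal 10% (sides balanced) to 87% (all 16 shifted by 1.0 residual SD in one direction, equal variances). The documents do not say where in that range the trial sits.

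The primary result is untouched. What improves is the ability to say whether a lower percentage change reflects the CA response or its denominator. That makes this a near-free improvement rather than a defect that threatens the trial.

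**What to change.** In SAP 17.2.2, add six comparisons to the absolute-value analysis: pre-CA at 3 h for D1, D2 and D3, each minus placebo pre-CA at 3 h, and the same three at 24 h. They take the form of rows 1-6. State that any conclusion about a drug effect on resting flow rests on these.

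Keep rows 7-14, labelled as descriptive. They still show the within-period change, so there is no need to remove them. State which forearm supplies the 0 h value and how the side is chosen in the first period.

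The cost is six more ESTIMATE statements and six more supplementary comparisons per method and CA concentration. For two methods and the 10% and 3% concentrations that is 6 × 2 × 2 = 24. No new measurements are needed, and under the SAP model the standard error is the same as for the rows already planned.

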9.7. Genetics

Not applicable.

9.8. Biomarkers

Not applicable.

9.9. Health Economics

Not applicable.

10. Statistical Considerations and Data Analysis

10.1. Sample Size Determination

The sample size is justified based on the statistical power to meet the primary endpoint of DBF measurements from LDI assay at t_{max} . The power calculation used 10% CA-induced absolute DBF in comparison between LY3526318 and placebo arms. For a 20% reduction in DBF (assuming mean observed placebo DBF of 444.3 arbitrary perfusion units (PU) with standard deviation of 55.1 PU) and a significance level of 0.05, a paired t-test with 16 patients results in 98% power to reject the null hypothesis. Incorporating a Bonferroni adjustment to account for multiplicity (changing the significance level to 0.05/3) lowers the power slightly to 96%.

10.2. Populations for Analyses

10.2.1. Study Participant Disposition

All participants who discontinue from the study will be identified, and the extent of their participation in the study will be summarized by treatment. If known, a reason for their discontinuation will be given.

10.2.2. Study Participant Characteristics

Participant demographics (age, race, ethnicity, height, and weight) will be summarized by treatment.

10.2.3. Concomitant Medications

Concomitant medications will be listed.

10.3. Statistical Analyses

Statistical analysis of this study will be the responsibility of Lilly or its designee.

Additional exploratory analyses of the data will be conducted as deemed appropriate. Study results may be pooled with the results of other studies for population PK and PK/PD analysis purposes.

For continuous variables, summary statistics will include number of participants, mean, median, standard deviation, minimum, and maximum. Categorical endpoints will be summarized using number of participants, frequency, and percentages. Additional analyses of the data will be conducted as deemed appropriate and may be fully detailed in a statistical analysis plan.

10.3.1. Safety Analyses

All study drug and protocol procedure AEs will be listed, and if the frequency of events allows, safety data will be summarized using descriptive methodology. Summary statistics for AE and SAE will be provided by dose level and for all placebo participants combined.

Safety assessments include laboratory tests, vital signs, ECGs, and physical examination. The parameters will be listed and summarized using standard descriptive statistics. Additional analysis will be performed as required.

10.3.2. Pharmacokinetic Analyses

Pharmacokinetic data will be presented as LY3526318 and M6 plasma concentration summaries.

10.3.3. Pharmacodynamic Analyses

The primary endpoint is the percent change from pre-CA to CA-induced DBF as measured by LDI, compared to placebo at 3 hours post-dose. Summary statistics for each cohort will be provided by treatment. Mixed-effect model for repeated measure (MMRM) will be used to evaluate the primary endpoint including covariates such as treatment, period, carry-over, and sequence. Similar analyses will also be conducted for LDI at 24 hours post dose as well as DBF outcomes as measured by LSCI (laser speckle contrast imaging) at 3 hours and 24 hours.

10.3.4. Pharmacokinetic/Pharmacodynamic Analyses

Pharmacokinetic and PD data may be combined with PK data from previous studies, to perform population PK/PD analyses in order to inform the design of future studies.

Appendix 1. Abbreviations and Definitions

Term	Definition
AE	adverse event: Any untoward medical occurrence in a patient or clinical investigation participant administered a pharmaceutical product that does not necessarily have a causal relationship with this treatment. An AE can therefore be any unfavorable and unintended sign (including an abnormal laboratory finding), symptom, or disease temporally associated with the use of a medicinal (investigational) product, whether or not related to the medicinal (investigational) product.
ALP	alkaline phosphatase
ALT	alanine aminotransferase
AST	aspartate aminotransferase
blinding	A procedure in which one or more parties to the study are kept unaware of the treatment assignment(s). Unless otherwise specified, blinding will remain in effect until final database lock.
	A single-blind study is one in which the investigator and/or his staff are aware of the treatment but the participant is not, or vice versa, or when the sponsor is aware of the treatment but the investigator and/his staff and the participant are not. A double-blind study is one in which neither the participant nor any of the investigator or sponsor staff who are involved in the treatment or clinical evaluation of the participants are aware of the treatment received
CA	cinnamaldehyde
CNS	central nervous system
CRU	clinical research unit
C-SSRS	Columbia-Suicide Severity Rating Scale
DBF	dermal blood flow
enroll	The act of assigning a participant to a treatment. Participants who are enrolled in the study are those who have been assigned to a treatment.
enter	Participants entered into a study are those who sign the informed consent form directly or through their legally acceptable representatives.
ECG	electrocardiogram
ED	early discontinuation
ERB	ethical review board
FIH	first-in-human
FU	safety follow-up
GCP	good clinical practice
HIV	human immunodeficiency virus

IB	Investigator's Brochure
ICF	informed consent form
ICH	International Council for Harmonization
IND	Investigational New Drug: An application to the FDA to allow testing of a new drug in humans.
informed consent	A process by which a participant voluntarily confirms his or her willingness to participate in a particular study, after having been informed of all aspects of the study that are relevant to the participant's decision to participate. Informed consent is documented by means of a written, signed and dated informed consent form.
IRB	institutional review board
investigator	A person responsible for the conduct of the clinical study at a study site. If a study is conducted by a team of individuals at a study site, the investigator is the responsible leader of the team and may be called the principal investigator.
LSCI	laser speckle contrast imaging
LDI	laser Doppler imaging
randomize	the process of assigning participant to an experimental group on a random basis
PK/PD	pharmacokinetic/pharmacodynamic
SAD	single ascending dose
SAE	serious adverse event
screen	The act of determining if an individual meets minimum requirements to become part of a pool of potential candidates for participation in a clinical study.
SUSARs	suspected unexpected serious adverse reactions
TEAE	treatment-emergent adverse event: Any untoward medical occurrence that emerges during a defined treatment period, having been absent pretreatment, or worsens relative to the pretreatment state, and does not necessarily have to have a causal relationship with this treatment
TBL	total bilirubin
TRPA1	Transient receptor protein ankyrin 1
ULN	upper limit of normal
WOCBP	woman of child-bearing potential

Appendix 2. Clinical Laboratory Tests

Safety Laboratory Tests

Hematology	Clinical Chemistry
Hematocrit	Sodium
Hemoglobin	Potassium
Erythrocyte count (RBC)	Glucose (fasting)
Mean cell volume	Blood urea nitrogen (BUN)
Mean cell hemoglobin	Total cholesterol
Mean cell hemoglobin concentration	Total protein
Leukocytes (WBC)	Albumin
Platelets	Total bilirubin
Differential WBC (Absolute counts and %) of:	Alkaline phosphatase (ALP)
Neutrophils	Aspartate aminotransferase (AST)
Lymphocytes	Alanine aminotransferase (ALT)
Monocytes	Creatinine
Eosinophils	Gamma-glutamyl transferase (GGT)
Basophils	
Alcohol breath test (ethanol)^c	
Urine Drug Screen^a	
Specific gravity	Nicotine metabolites
pH	Amphetamine (including XTC)
Protein	Barbiturates
Glucose	Benzodiazepine
Ketones	Cannabinoids
Bilirubin	Cocaine
Urobilinogen	Methadone
Blood	Opiates
Nitrite	
RBC and WBC counts	Hepatitis B surface antigen
	Hepatitis C antibody
	HIV ^b
	FSH
	Pregnancy Test (Serum, Quantitative β -hCG)

Abbreviations: β -hCG = beta subunit of human chorionic gonadotropin; FSH = follicle-stimulating hormone; HIV = human immunodeficiency virus; RBC = red blood cells; WBC = white blood cells.

^a Urine drug screen may be repeated prior to admission to the clinical research unit and at other times indicated in the Schedule of Activities.

^b Performed at screening only

^c Breath sample for ethanol test may be repeated prior to admission to the clinical research unit and at other times indicated in the Schedule of Activities.

